2.3.2.2 All Bleeds

Given that some patients may report bleeds that they did not treat, ‘all bleeds’ will be analyzed as an additional endpoint definition to treated bleeds and comprise both treated and non-treated bleeds. In this definition, all bleeds are included, irrespective of treatment with coagulation factors, with the following exception: Bleeds due to surgery/procedure are excluded as for the ‘treated bleed’ analysis.

The endpoint of all bleeds fulfills the adapted ISTH criteria, as described in the protocol and the 72-hour rule, in particular. For treated bleeds, it is implemented exactly as defined for the ‘treated bleed’ definition (see Section [2.3.2.1](#)). For non-treated bleeds (not followed by any treatments with coagulation factors before the recording of a subsequent bleed), it is implemented by calculating a treatment-free period of 72 hours from the bleed itself.

2.3.2.3 Treated Spontaneous Bleeds

In the analysis of spontaneous bleeds, only treated bleeds that fulfill the 72 hour rule are included.

Bleeds are classified as “spontaneous” if there is no other known contributing factor such as trauma or procedure/surgery.

2.3.2.4 Treated Joint Bleeds

In the analysis of treated joint bleeds, only treated bleeds that fulfill the 72 hour rule are included. Bleeds due to procedure/surgery are, again, excluded. Joint bleeds are defined as bleeds where the bleed type is “joint”.

2.3.2.5 Treated Target Joint Bleeds

Target joints are major joints into which repeated bleeds occur (i.e., ≥ 3 bleeds into the same joint over the last 24 weeks prior to study entry).

The target joints prior to study entry are identified through the eCRF. The bleeds in target joints during the efficacy period are defined by first selecting the bleeds that fulfill the definition of a treated joint bleed (see Section 2.3.2.4) and then counting how many of these occurred in a target joint prior to study entry. The locations to be taken into account are: shoulder, elbow, wrist, fingers/thumb, hip, knee, ankle, sole/heel, and toes. Left and right side of the same joint type are considered to be separate joints.

2.3.2.6 Intra-Patient Comparison

In the intra-patient comparison (on All Bleeds and on Treated Bleeds), only patients who participated in the NIS BH29768 are included. This is because it is possible to apply the detailed definition only if the data are collected with the same granularity for both time periods. Of note, for some patients who participated in NIS BH29768, the total time in that study prior to enrolment in Study BH29992 may be short.

The efficacy period in NIS BH29768 is defined as the time from the first entry on the electronic, handheld device or site data entry system to the day before the patient is enrolled in Study BH29992. Usually, the date of the first entry is the date the Training Module on the electronic, handheld device is completed.

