2.1 EFFICACY OBJECTIVES

The endpoints will be analyzed separately for the three cohorts: Cohort A (1.5 mg/kg QW), Cohort B (3 mg/kg Q2W), and Cohort C (6 mg/kg Q4W), and overall as appropriate.

The efficacy objectives for this study are as follows:

- To evaluate the clinical effect of prophylactic emicizumab on the number of bleeds over time (i.e., bleed rate) *
- To evaluate the efficacy in reducing the number of bleeds over time compared with the patient's historical bleed rate (intra-patient comparison, *Cohort A only, as patients enrolled in Cohorts B and C will not have previously participated in the non-interventional study*) *
- To characterize the efficacy of up-titration on *an* intra-patient level, *based on the basis of the number of bleeds over time* *
- To evaluate the HRQoL of children 8–17 years of age according to Haemo-QoL-Short Form (SF) (completed by patients)
- To evaluate proxy-reported HRQoL and aspects of caregiver burden using the Adapted InhibQoL Including Aspects of Caregiver Burden questionnaire for all children (completed by caregivers)
- To assess the number of days missed from daycare/school and days hospitalized

* Analyses will be performed for: treated bleeds, all bleeds, treated spontaneous bleeds, treated joint bleeds, and treated target joint bleeds.

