6.4.1 Efficacy Endpoints

One efficacy objective is to evaluate the clinical effect of prophylactic emicizumab on the number of bleeds over time. *This analysis will be performed for each cohort separately*

as well as overall as appropriate. Another objective is to characterize the efficacy up-titration on an intra-patient level. The comparison between historical and on-study treatment period for bleeds over time will also be evaluated for patients who were previously enrolled in Study BH29768. *These patients will enroll exclusively in Cohort A, therefore this intra-patient analysis will be conducted only in patients receiving the 1.5 mg/kg QW maintenance dose.* The definition of a bleed is described in Section 4.7.8. All definitions (i.e., treated bleeds, all bleeds, treated spontaneous bleeds, treated joint bleeds, treated target joint bleeds) will be evaluated for each of the efficacy objectives.

Characterizing the effect of emicizumab on-study treatment period for bleed over time as well as analyses of up-titration and the comparison between historical and on study treatment period for bleed over time will be performed *for Cohort A and for the overall analysis* using a negative binomial regression model, which accounts for different follow-up times, with the patient's number of bleeds as a function of the time that each patient stays in the study included as an offset in the model.

The number of bleeds will be also annualized (Annualized Bleeding Rate—ABR) *for Cohorts B and C as well as* for each patient using the following formula:

$$\text{ABR} = \left(\frac{\text{Number of bleeds during the efficacy period}}{\text{Total number of days during the efficacy period}} \right) \times 365.25$$

Of note, if the convergence of the negative binomial model is not achieved or is questionable, the efficacy analysis will be based on the ABR (formula just above).

The number of bleeds, sites of bleeds, and types of bleeds will be summarized for all patients and listed for each patient individually. Several exploratory analyses will be conducted to characterize the type, location, duration, frequency, and pattern of bleeds. For continuous endpoints, descriptive statistics will be calculated and categorical endpoints will be characterized through frequency tables.

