Efficacy endpoints will be analyzed separately by cohort (i.e., Cohort A: 1.5 mg/kg QW; Cohort B: 3 mg/kg Q2W; Cohort C: 6 mg/kg Q4W) and overall as appropriate. Patients who require up-titration will be reported in their original maintenance dose group, and a listing based on their up-titration period will be provided. A detailed description of the statistical methods that will be used for the efficacy analyses will be provided in the SAP.

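### The SAP plans the comparison with pre-emicizumab bleeding for two bleed definitions where the protocol calls for five, and gives no reason

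*SAP*

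**What the plan says.** Protocol 2.1 states the objective "To evaluate the efficacy in reducing the number of bleeds over time compared with the patient's historical bleed rate". It applies to Cohort A only and carries an asterisk, whose footnote reads "Analyses will be performed for: treated bleeds, all bleeds, treated spontaneous bleeds, treated joint bleeds, and treated target joint bleeds". Protocol 6.4.1 takes up the historical comparison for patients from the NIS and, in the same paragraph, says that all definitions are in scope: "treated bleeds, all bleeds, treated spontaneous bleeds, treated joint bleeds, treated target joint bleeds) will be evaluated for each of the efficacy objectives". It names a negative binomial (NB) model for the comparison, and an analysis based on the annualized bleeding rate (ABR) if convergence fails or is questionable.

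SAP 2.3.2.6 sets a narrower scope in its opening words, "In the intra-patient comparison (on All Bleeds and on Treated Bleeds", and includes only patients from the NIS. SAP 4.4.1.2 points only to the treated and all-bleeds definitions and fits an NB model with a repeated statement to estimate the rate ratio. SAP 2.3.2.3 to 2.3.2.5 define treated spontaneous, treated joint and treated target joint bleeds, but no body text compares them with history. SAP Appendix 1, the copied synopsis, still has the asterisked objective and the five-definition footnote.

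**The concern.** The SAP body is narrower than the protocol and than the SAP's own appendix, and does not acknowledge it. An analyst who follows SAP 2.3.2.6 and 4.4.1.2 will report the before-and-after comparison for treated and all bleeds and nothing for the other three definitions.

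This is the only planned comparison with bleeding before emicizumab. There is no control arm, and Cohorts B and C have no NIS data. Whether spontaneous or joint bleeding fell relative to a patient's own prior rate is part of the protocol's objective, and the SAP as written would leave it unanswered.

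**Working it through.** No formula or stated figure is in question, so the check sets the texts side by side and counts definitions.

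| Place | Definitions for the historical comparison |
|---|---|
| Protocol 2.1 (asterisk and footnote) | 5 |
| Protocol 6.4.1 | 5 |
| SAP Appendix 1 (synopsis) | 5 |
| SAP 2.3.2.6 | 2 |
| SAP 4.4.1.2 | 2 |

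Not covered in the SAP body: 5 − 2 = 3 (treated spontaneous, treated joint, treated target joint).

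**Is a reason given?** SAP 2.3.2.6 has one explanatory sentence, about needing data of equal detail in both periods. It explains why only NIS patients are used, not why only two definitions are. SAP Section 2 says that the SAP outlines certain differences, but these are between the interim study report and the final analyses, not between SAP and protocol.

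**Can spontaneous and joint bleeds be compared?** The retained treated-bleed definition (SAP 2.3.2.1) already uses bleed type and anatomical location for the 72-hour rule, and cause to exclude bleeds from surgery or procedures. Joint bleeds are identified by type (SAP 2.3.2.4) and spontaneous bleeds by cause (SAP 2.3.2.3). If treated bleeds can be derived in both periods, as SAP 2.3.2.6 implies, these two should be derivable as well.

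**Can target joint bleeds be compared?** Not on the same footing. A target joint is one with at least 3 bleeds in the 24 weeks before study entry (SAP 2.3.2.5). The NIS comparator period ends the day before enrolment (SAP 2.3.2.6). If a patient has T weeks in the NIS, the share of the comparator period that falls inside the selection window is min(T, 24)/T. The documents do not give T, so these values are assumed:

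- T = 12: 12/12 = 100%
- T = 24: 24/24 = 100%
- T = 48: 24/48 = 50%

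The protocol says that the NIS may supply over 24 weeks of data, and the SAP says that some patients' time may be short, so the overlap could be complete for some patients. With T = 24, and if the qualifying bleeds were all recorded in the NIS as treated, each target joint would enter with a historical rate of at least 3/(24 × 7) × 365.25 = 6.5 bleeds per year purely through selection. Some fall on study is then expected from regression to the mean alone. SAP 2.3.2.5 also defines these bleeds only for the on-study efficacy period and has no rule for the NIS period.

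**Is the narrowing confined to this objective?** No. Protocol 2.1 puts the same asterisk on the up-titration objective, and SAP 2.3.2.7 limits that analysis to treated and all bleeds: again 5 − 2 = 3 not covered.

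**The case against.** The best defence has four parts. The study is entirely descriptive. The three missing definitions are subsets of treated bleeds, whose comparison is kept. Their on-study definitions remain in the SAP. And the protocol leaves detail to the SAP: "A detailed description of the statistical methods that will be used for the efficacy analyses will be provided in the SAP". The first three are true and keep the point small. The fourth does not help, because the sentence passes on methods, not the choice of definitions.

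The target joint problem is also a sound reason not to run that comparison as a model-based effect estimate. It stands, but the SAP does not offer it as its reason, and it does not apply to spontaneous or joint bleeds.

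A reader might infer more than the texts support:

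- *That the SAP has removed the three comparisons.* It never says so, and Appendix 1 still lists all five. They are unspecified in the body.
- *That this is the only comparative efficacy analysis.* It is not. Up-titration is a separate intra-patient analysis (SAP 2.3.2.7), and SAP 4.4.2 plans comparative subgroup analyses.
- *That running the three later would be data-driven.* They are listed in Protocol 2.1, Protocol 6.4.1 and SAP Appendix 1, and the protocol names the model and its fallback. Carrying them out would follow the protocol.

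**Conclusion.** The inconsistency is real. The protocol calls for the historical comparison on five definitions and the SAP body specifies two without explanation. Three of five listed comparisons, or 60%, are unplanned. That figure counts definitions; it does not measure bias or lost precision. No error rate or sample size is affected, so this is a minor point, but following the SAP leaves part of a stated efficacy objective unanswered.

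The conclusion that spontaneous and joint bleeds can be added rests on the SAP's implication that NIS data have the same detail as on-study data. The NIS documents were not available to confirm this.

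**What to change.** In SAP 2.3.2.6 and 4.4.1.2:

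- Add treated spontaneous and treated joint bleeds, using the same repeated-measures NB model as for treated and all bleeds.
- State the protocol's ABR-based analysis as the fallback if the model does not converge or is questionable; SAP 4.4.1.2 currently names no such fallback. A pooled count over patient-time with an exact Poisson interval is not a good substitute, because it ignores variation between patients and the pairing of the two periods.
- Report treated target joint bleeds before and on study descriptively only. Note that joints are selected on pre-entry bleeding in a window that can overlap the NIS period, so some fall is expected from regression to the mean.

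Align SAP 2.3.2.7 with Protocol 2.1 for up-titration in the same amendment. If the sponsor prefers a narrower set for either objective, the SAP should state this as a change from the protocol and give the reason.

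The cost is a few extra model runs or descriptive rows. Some counts will be sparse, and those estimates will be imprecise.

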In a first interim data review, the appropriateness of the initial dosing regimen will be evaluated (maintenance dose of 1.5 mg/kg QW) after the first 3–5 patients (≥ 2 to < 12 years of age) have been dosed for a minimum of 12 weeks. A Joint Monitoring Committee (JMC; see Section 9.5) will review all cumulative data (e.g., safety, efficacy, and pharmacokinetics) to provide recommendations on increasing the starting maintenance dose (if necessary) to target a similar plasma emicizumab trough concentration as the one being targeted in adolescents and adults (i.e., 45 $\mu\text{g}/\text{mL}$). All patients enrolled following the first interim data review will receive the starting maintenance dose selected by the JMC. Those patients enrolled prior to the first interim data review who had not had their dose up-titrated will remain on their current maintenance dose, unless they meet eligibility for up-titration based on protocol-defined criteria (see Section 4.5.2).

In order to include and safely treat the youngest patients (birth to < 2 years of age), this study will include a staggered approach to enrollment by age. Patients ≥ 2 to < 12 years of age and patients 12–17 years of age who weigh < 40 kg will enroll first. A second interim data review will occur once at least 10 patients between ≥ 2 and < 12 years of age have been dosed for a minimum of 12 weeks, at which time all cumulative data (e.g., safety, efficacy, and pharmacokinetics) will be evaluated to provide recommendations for enrollment of children < 2 years of age, as well as on any additional adaptations of the maintenance dose if necessary.

Furthermore, should patient recruitment be faster than anticipated, enrollment will be placed on a temporary hold following the first 20 patients until the JMC releases its recommendations on the appropriateness of the maintenance dose (*Cohort A*). After the JMC recommendations are released following both interim data reviews, the study will continue to enroll in *Cohort A* up to approximately 60 patients.

[figure not shown]

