2.3 OBJECTIVES AND ENDPOINTS

2.3.1 Efficacy Period for All the Endpoints

The start of the efficacy period for each individual patient is defined as the day of the first emicizumab dose.

The end of the efficacy period is defined as the date of the clinical cutoff or the date of withdrawal from the initial study period (i.e., treatment period according to eCRF), whichever is earlier. For patients who withdraw from the study before reaching the Week 1 visit, the duration of efficacy period is set to 1 day and it starts and ends on the day of enrolment.

For patients whose dose is up-titrated, the bleeds on the up-titrated dose are analyzed separately. The efficacy period on a given up-titrated dose starts with the first day on this dose and ends on the day of the clinical cut-off, the date of withdrawal, or on the last day on this specific dose, whichever is earlier.

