4.2.3 Non-Interventional Population

This population includes patients who participated in Cohort B of the NIS BH29768 prior to enrolment to this study. All the NIS patients enrolled in BH29992 are enrolled to Cohort A.

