4.4.1 Efficacy Endpoint

4.4.1.1 Bleed Rate

A bleed is defined in two ways. The first definition uses adapted ISTH definition of a bleed ([Blanchette 2014](#); see Section [2.3.2.1](#); see Protocol Section 4.7.8). The second definition is counting all the bleeds regardless of the treatment (see Section [2.3.2.2](#)).

The number of bleeds over time (bleed rate) will be calculated using a negative binomial (NB) regression model, which accounts for different follow-up times, with time that each patient stays in the study (efficacy period) included as an offset in the model. In addition, the number of bleeds will also be annualized for each patient using the following formula:

$$ABR = (Number\ of\ bleeds/number\ of\ days\ during\ the\ efficacy\ period) \times 365.25.$$

For the interim CSRs, the population ABR may not be robust as it might be driven by only a few extreme observations because of the short follow up time. Therefore, the bleed rate will be characterized through individual patient data collected on the BMQ. In addition, with such short follow up, the NB model might not converge or the results might be unreliable. For all the patients, the number of bleeds will be described with use of descriptive statistics. The individual ABR will be calculated for patients who have been on the study for at least 12 weeks on the same dose (including the loading doses) with use of the given formula above.

The number of bleeds, types, and locations of bleed will be summarized for all patients and listed for each patient individually. Several exploratory analyses will be conducted to characterize the type, location, frequency, and pattern of bleeds.

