4.4.1.2 Intra-Patient Comparison

The definition of treated bleeds and all bleeds is described in Section [2.3.2](#). The analysis methodology is the NB regression model.

This analytic model estimates the rate ratio, λ_t/λ_c , which quantifies the risk of bleeding associated with prophylactic emicizumab (λ_t) in comparison to the historical bleeding events (λ_c). The analysis will be performed overall and for each dose titration.

The treatment effect therein is based on a repeated statement in the model with use of the SAS GENMOD procedure. Bleed rates for prophylactic emicizumab and no prophylaxis and the rate ratio will be presented and include 95% confidence intervals.

The intra-patient comparison will be performed on patients who have been enrolled at least 12 weeks before the cut-off.

For the Interim CSR, individual patient's ABR will be provided in a descriptive manner including the reduction in ABR comparing before and after entering into Study BH29992. At this stage, the patients included in the analysis will have been on the study for at least 12 weeks.

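### The historical (NIS) bleed period has no stop at NIS completion or withdrawal, so a child who left the NIS before enrolling would carry unobserved days into the offset as bleed-free time

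*SAP*

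**What the plan says.** The intra-patient comparison is limited to children who took part in the non-interventional study (NIS) BH29768. SAP 4.2.3 describes them as "patients who participated in Cohort B of the NIS BH29768 prior to enrolment to this study", and all of them are in Cohort A of this trial.

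- **Historical period (SAP 2.3.2.6).** It starts at the first entry on the handheld "device or site data entry system to the day before the patient is enrolled in Study BH29992". No earlier end date is given.
- **On-study period (SAP 2.3.1).** It starts at the first dose and ends at "the date of the clinical cutoff or the date of withdrawal from the initial study period", whichever comes first.
- **Use of the period (SAP 4.4.1.1).** The model has the "time that each patient stays in the study (efficacy period) included as an offset in the model", and the same number of days is the denominator of each child's ABR.
- **Target quantity (SAP 4.4.1.2).** The same type of model gives a rate ratio that "quantifies the risk of bleeding associated with prophylactic emicizumab" against the historical rate, with a 95% confidence interval. In the interim report, each child's before-and-after ABR is described individually.
- **Missing data (SAP 4.8).** The section deals with completeness of a single questionnaire and with missing clock times. It does not deal with weeks in which nothing was recorded. SAP 4.3 evaluates diary compliance as part of study conduct but does not link it to the length of the efficacy period.

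**The concern.** The two periods that form one rate ratio close by different rules. On study, a child who withdraws stops contributing exposure. In the historical period, a child who completes or withdraws from the NIS keeps contributing exposure until the day before enrolment in BH29992, although bleeds may no longer be collected. Those days enter the offset as bleed-free, when in truth they are unobserved.

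This is the only planned comparison of bleeding on emicizumab with bleeding before it. The study has no hypothesis test, so the estimated ratio and its interval are the result. SAP 2.3.2.6 justifies the restriction to NIS participants by the need for equally detailed data in both periods, and a different closing rule works against that aim. Any effect would depend on how the transfer between studies was organised and not on bleeding. In the individual ABR listings no averaging would soften it.

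**Working it through.** The documents give no historical rate, rate ratio, number of NIS children or gap length, so there is no planned figure to reproduce. The check is of the rule itself.

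**Step 1: dilution factor.** Let a child bleed at true annual rate λ, be observed for O weeks, and have G further weeks before enrolment in which nothing is collected.

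- Bleeds recorded = λ × 7·O / 365.25
- ABR under the SAP rule = bleeds / (7·(O + G)) × 365.25 = λ × O/(O + G)
- Rate ratio under the SAP rule = true ratio × (O + G)/O

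With G = 0 both factors are 1.

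**Step 2: numbers for one child.** Protocol 3.1 says that the NIS may provide more than 24 weeks of data, and SAP 2.3.2.6 warns that NIS time may be short for some children, so O is set to 24 and 12 weeks. The historical ABR of 8 is borrowed from the benchmark for prophylactic bypassing agent in Protocol 3.3.1. It is not an NIS planning value. The gap lengths and the true ratio of 0.20 are assumptions.

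| Observed (wk) | Gap (wk) | O/(O+G) | Historical ABR (true 8) | Rate ratio (true 0.20) |
|---|---|---|---|---|
| 24 | 0 | 1.00 | 8.00 | 0.200 |
| 24 | 6 | 24/30 = 0.80 | 6.40 | 0.250 |
| 24 | 12 | 24/36 = 0.67 | 5.33 | 0.300 |
| 12 | 6 | 12/18 = 0.67 | 5.33 | 0.300 |
| 12 | 12 | 12/24 = 0.50 | 4.00 | 0.400 |

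**Step 3: pooled estimate.** The table applies to an affected child. To see the pooled effect, a repeated-measures negative binomial model with a log-time offset was simulated with 20 children, 24 NIS weeks, 52 on-study weeks, dispersion 1, true historical rate 8, true ratio 0.20 and 300 runs per scenario. All of these settings are assumptions. Medians:

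| Share with a gap | Gap (wk) | SAP rule: rate, ratio | Period ended when observation ended: rate, ratio |
|---|---|---|---|
| 25% | 8 | 7.33, 0.211 | 7.83, 0.198 |
| 50% | 8 | 6.82, 0.229 | 7.83, 0.200 |
| 50% | 12 | 6.48, 0.243 | 7.94, 0.200 |
| 100% | 8 | 5.91, 0.267 | 7.88, 0.200 |

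The last row agrees with the formula: 0.20 × 32/24 = 0.267.

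**Step 4: which part is asymmetric.** Withdrawal closes the on-study period but not the NIS period. A lapse in diary entry by a child still in the study closes neither. The difference between the periods is therefore confined to leaving the NIS.

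**The case against.** The strongest reply is that the situation may never arise. Protocol 3.1 describes children who are currently in the NIS as eligible for this trial, which suggests direct transfer. If each child stayed under observation until transfer, the day before enrolment is the correct end date. This stands: nothing in the documents shows a gap for any child. The NIS protocol is not available, and late entries through the site system could fill an apparent gap.

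Three stronger readings are tempting and are not supported.

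- **Gaps can be inferred from the wording or the enrolment rules.** Protocol 6.4.1 speaks of "patients who were previously enrolled in Study BH29768", but that gives only the order of the studies. Protocol 3.1 provides that "enrollment will be placed on a temporary hold following the first 20 patients" if recruitment is fast, and children under 2 had to wait for the JMC recommendation. Both delay entry to BH29992, but neither ends NIS follow-up. A child waiting inside the NIS gains observed time. The interval from the 28 October 2016 data cutoff to the 7 December 2016 recommendation is not a diary gap either.
- **Lapsed diary entry is handled unequally.** It is handled alike, because neither period is censored for it.
- **The rule flatters the drug.** It does the opposite: a diluted historical rate raises the ratio of treated to historical bleeding, so the error is conservative.

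That the bias is conservative, and the analysis descriptive, lowers the stakes. It does not make the rule right: in a study whose product is an estimate with an interval, a shift caused by transfer timing should not be left in when one clause removes it.

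**Conclusion.** The rule is incomplete as written. For any child who left the NIS before enrolling in BH29992, it counts unobserved days as bleed-free exposure, multiplies that child's historical rate by O/(O + G), and moves the rate ratio toward 1. With 24 observed weeks the factor is 0.80 for a 6-week gap and 0.67 for a 12-week gap. In the simulated pooled analyses a true ratio of 0.20 became 0.211 to 0.267.

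These sizes rest wholly on assumed gaps, and the simulation also on an assumed number of children, dispersion and true ratio. The actual effect is unknown, and it is zero if every child was followed in the NIS until transfer. The documents support saying that the historical rate could be too low if a gap occurred. They do not support saying that it is too low. The change is worth making because it is specific and nearly free, and because it lets the report state whether gaps existed.

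**What to change.** In SAP 2.3.2.6, define the end of the NIS efficacy period as the earlier of (a) the date of NIS completion or withdrawal and (b) the day before enrolment in BH29992. This mirrors SAP 2.3.1, where exposure stops at "the date of withdrawal from the initial study period (i.e., treatment period according to eCRF), whichever is earlier". Report the gap for each child, in days from the end of NIS participation to enrolment, including a statement if all gaps are zero.

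Do not end the primary NIS period at the last diary entry unless the same rule is applied on study. Used on one side only, it would create a new asymmetry. Because entries are prompted by bleeds as well as weekly, it could also tie the end date to a bleed and raise the historical rate. It is suitable as a sensitivity analysis applied to both periods, counting confirmed no-bleed weeks where these exist. SAP 2.2 describes such weekly confirmations for the BH29992 questionnaire; whether the NIS collected them needs checking.

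The cost is one sentence and one derived date, assuming that the NIS database holds the date of completion or withdrawal. The small downside is slightly less historical follow-up for any child with a gap.
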